## **Group Cohort**

This group will be composed by 150 MS patients who, consecutively, from the start of the study, will refer to the MS clinic of the Neurology Unit of the Ferrara University Hospital, Italy. The first 50 patients with a PACQoL score  $\geq 32$  will be asked to be willing to enter the next phase of the study that continues at the Coloproctological Outpatient Clinic of Ferrara University Hospital, Italy with an appointment provided by the neurologist with a pre-established schedule (with written consent).

## **Intervention**

Patients with severe intestinal dysfunction impairment (PAC QoL score  $\geq 32$ ) will be offered the adoption of the TAI (Transanal Irrigation) with Peristeen Device as a way to manage their own evacuation, replacing any other measure used until that moment (suppositoires, enemas) with the exception of the possible intake of macrogols and/or prebiotics and/or probiotics which instead patients can continue. This treatment will be proposed to all patients with severe impairment of intestinal function.

The TAI training with Peristeen will be carried out at the surgical clinic of the Surgical Department of the Ferrara University Hospital, Italy, by the health personnel involved in the study, usually in a single session, but more sessions may be necessary, documented in CRF as VISIT 3, VISIT 3 bis and so on, until the end either with the continuation of the TAI independently for 4 weeks or with patient's exclusion from the study if the guarantees of appropriate use of the device will not be reached.

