Patients with PacQol score  $\geq 32$  will be sent to the surgical clinic for the second phase. During the latter phase, patients will undergo a number of visits varying from 1 to 4 depending on the patient's willingness to continue the study. After the illustration of the purpose and protocol of the study to the patient,

classification of constipation and/or faecal incontinence in accordance with the Rome III Diagnostic Criteria will be assessed, with consideration of other possible etiopathogenetic factors other than MS. Further questionnaires will be filled in to evaluate the disease status (Constipation scoring system by Agachan-Wexner, Obstructed defecation score by Altomare et al, Fecal Incontinent grading scale by Jorge-Wexner); if the patient will consent to the continuation of the study, he will be given 7-days food diaries, evacuation diaries, radiopaque markers, stool collection container and appointment date for plain abdominal X-ray which may coincide with the appointment for examination number 2 (visit 2 or 3).

In particular, radiopaque markers Intestinal Transit Study will be performed according to the Bouchoucha procedure revised by Abrahamsson, which involves ingestion of 10 markers for 6 days at the same time and execution of a plain abdominal X-ray on the 7th day. During this week the patient will complete an evacuation diary recording the time and number of evacuations, the method of eventual bowel care, the consistency of faeces according to the Bristol Scale, any episode of fecal incontinence, the type of hygiene measures in general, the number of enemas, diapers, and any other garrison used in relation to the evacuation.

Patients will be asked to collect a faecal sample in a container during the last week before the following inspection at Visit 2.

During the second visit, the outcome of the plain abdominal X-ray will be discussed, the completed diaries will be collected, and the faecal sample will be stored at -20 C° and subsequently sent to the Laboratory of the Department of Pharmacy and Biotechnology of the University of Bologna, Italy for the analysis of the intestinal microbiome composition.

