Patients with severe NBD impairment will be offered the adoption of TAI as a way to manage their own evacuation, replacing any other measure used until that moment (suppositoires, enemas) with the exception of the possible intake of macrogols and/or prebiotics and/or probiotics which instead can be continued. This treatment will be proposed to all patients with severe impairment of intestinal function.

The TAI training with Peristeen will be carried out at the surgical clinic of the Surgical Department of the Ferrara University Hospital, Italy, by the personnel involved in the study, usually in a single session, but more sessions may be necessary.

During the following 4 weeks, patients will continue to use the Peristeen at home according to the instructions provided by the training staff collecting a stool sample each week. During the last of the four weeks of TAI use patients will repeat the compilation of food diaries, evacuation diaries, the radiopaque markers Transit Time, and collection of the stool for microbiota analysis. The appointment for the radiography could coincide also in this case with the following visit (visit 3 or 4).

During the last visit the outcome of Transit Time X-ray will be discussed, completed diaries and stool samples will be collected, and PAC-QoL questionnaire will be submitted to patients who completed the study pathway.

Patients will be asked about overall satisfaction of TAI treatment with Peristeen by means of a numerical assessment from 0 to 10.

Finally, any comment will be noted as well any events that might be related to TAI irrigation with Peristeen will be recorded.

Patients will undergo a neurological examination 3 months after the start of treatment.

The whole duration of the study will be of 2 years.

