## **Secondary Outcome Measures**

- 1) Correlation between Intestinal Transit Time and constipation scores in MS patients with intestinal dysfunction. To calculate the Correlation Coefficient between Intestinal Transit Time and the Bristol Score, the Agachan-Wexner Score, the Cleveland Clinic Index, and the NBD Score.
- 2) Correlation between Diet and intestinal dysfunction in MS patients. To correlate the Intestinal Transit Time and the Bristol Scale Score to the type of diet usually followed by patients in terms of adequacy of caloric intake compared to BMI, composition of macronutrients, and dietary fibre intake.
- 3) Efficacy of TAI in MS patients with intestinal dysfunction. Compare the Scores of the assessment scales used before and after the 4-week TAI treatment period, in order to detect a reduction in severity and an improvement in QoL score. Calculate a possible advantage or non-benefit of the costs of treatment with TAI compared to the previous bowel management.
- 4) Analysis of Microbiota in MS patients with intestinal dysfunction, before and after treatment with TAI. Compare the composition of the intestinal microbiota of MS patients with the known "healthy"

profile of the Italian population of North East of Italy and assess any changes after the period of treatment with TAI.

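### Patients who fail TAI training leave the study and only pathway completers get the final PAC-QoL, so the before/after PAC-QoL result can describe trained completers only

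*Combined protocol and SAP*

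**What the plan says.** Four parts of the combined protocol and SAP bear on this.

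- **Intervention.** Training usually takes one session, with more if needed, each "documented in CRF as VISIT 3, VISIT 3 bis and so on". It ends either in 4 weeks of independent TAI or "with patient's exclusion from the study if the guarantees of appropriate use of the device will not be reached".
- **Study Protocol, last visit.** The "PAC-QoL questionnaire will be submitted to patients who completed the study pathway". The term is not defined. A later sentence adds: "Patients will undergo a neurological examination 3 months after the start of treatment". No questionnaire is attached to that examination.
- **Secondary Outcome Measures, item 3.** The title is "Efficacy of TAI in MS patients with intestinal dysfunction". The instruction beneath it is to "Compare the Scores of the assessment scales used before and after the 4-week TAI treatment period".
- **Statistical analysis.** The section lists tests, a Cox regression for predictors of improvement after TAI, and a cohort reporting standard. It gives no analysis set, no rule for missing post-TAI scores, and no statement that the numbers starting, failing and stopping will be reported.

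Two passages bear on how many patients might start. Under Group Cohort, "The first 50 patients with a PACQoL score" at or above 32 are invited to phase 2. Under Study Protocol, the number of phase 2 visits varies "depending on the patient's willingness to continue the study".

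**The concern.** Patients who cannot learn or sustain TAI have no planned final PAC-QoL, so they cannot enter the before/after comparison. A clinic deciding whether to offer TAI needs two things: how PAC-QoL changes in everyone who begins training, and what share cannot use the device. The plan supplies the change only in those for whom TAI worked well enough to finish, and does not commit to reporting the share.

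The introductory part of Study Protocol gives patients' compliance with TAI as something not yet established. Those who fail or stop are the most direct evidence on that question. Their scores have to be collected at the time, because no later analysis can recover a questionnaire that was never given.

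**Working it through.** **Step 1: who can have a final PAC-QoL under the plan.**

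| Patient who began training | Final PAC-QoL planned? | Basis |
|---|---|---|
| Fails training | No | Excluded from the study (Intervention) |
| Trained, stops during the 4 weeks | Most naturally no, but the term is undefined | Completers of the pathway only (Study Protocol) |
| Trained, completes 4 weeks | Yes | Study Protocol |

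The 3-month neurological examination may reach some patients who stopped, but it names no PAC-QoL. The cohort reporting standard governs the report and does not create scores. The PAC-QoL part of item 3 therefore rests on the last row, possibly with some patients from the second.

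**Step 2: what this could do to the result.** The documents give no figure to reproduce, so every input here is an assumption.

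- d = mean PAC-QoL change in completers
- f = share of starters who fail or stop
- r = mean change in those patients divided by d

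All-starter mean = (1 − f)·d + f·r·d. The ratio of the completer mean to the all-starter mean is 1/(1 − f + f·r).

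| f | r = 1 | r = 0.5 | r = 0 |
|---|---|---|---|
| 10% | 1.00 | 1/0.95 = 1.05 | 1/0.90 = 1.11 |
| 20% | 1.00 | 1/0.90 = 1.11 | 1/0.80 = 1.25 |
| 30% | 1.00 | 1/0.85 = 1.18 | 1/0.70 = 1.43 |

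Within this range r = 0 is the extreme. Patients are selected on a PAC-QoL score of at least 32, so non-users may improve through regression to the mean. Nothing in the documents confines r to 0–1, however. At f = 20%, r = 1.5 gives 1/(0.8 + 0.3) = 0.91, a completer result that is too unfavourable, and r = −0.5 gives 1/(0.8 − 0.1) = 1.43. The direction is therefore open as well as the size.

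**Step 3: how many patients.** Fifty are invited to phase 2 and continuation is voluntary, so starters may be fewer. Expected number without a final score = n·f:

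| Starters n | f = 10% | f = 20% | f = 30% |
|---|---|---|---|
| 20 | 2 | 4 | 6 |
| 30 | 3 | 6 | 9 |
| 50 | 5 | 10 | 15 |

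**Step 4: what contacting them would gain.** Let p be the share of non-completers who reply. If r among those still missing may lie anywhere from 0 to 1, the all-starter mean is uncertain by f·(1 − p)·d. At f = 20%:

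- p = 0: 0.20d
- p = 0.5: 0.10d
- p = 0.8: 0.04d

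A wider range for r widens all three in proportion.

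**Step 5: precision of the failure share.** The 95% Wilson interval for an assumed 10 of 50 is 11% to 33%; for 4 of 20 it is 8% to 42%.

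**The case against.** The strongest case against is that item 3 already defines its population. Its operative sentence compares scores around the 4-week TAI period, and someone who never reached independent use has no such period. On that view only a short title is wider than its definition, and an all-starter average in an uncontrolled study mixes TAI users with patients who have gone back to other bowel care.

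Much of this stands. A result in 4-week users is legitimate and should be kept. Ending TAI in a patient who cannot use the device properly is sound clinical practice. The term for pathway completion is undefined, so the loss of those who stop midway is a natural reading rather than an explicit rule; only exclusion after failed training is explicit. The magnitudes above rest wholly on assumptions.

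It does not dispose of the point. Ending treatment need not end follow-up, and the all-starter change answers the question of a clinic offering TAI, which the user result cannot. Relabelling and counting alone would show how many failed or stopped, but not how they fared.

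A reader might go further and infer that the TAI result is known to be inflated, that data from excluded patients are thrown away, or that failures cannot be counted. The documents support none of these. They give no outcome for non-completers. They nowhere say that collected data are discarded. They record each training session in the CRF.

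**Conclusion.** The point holds in a limited form. Followed as written, the plan makes the PAC-QoL part of Secondary Outcome Measures item 3 a trained-completer result under a title that is wider, and nothing elsewhere supplies the missing scores. This follows from a stated exclusion rule and a stated restriction on the questionnaire, not merely from brevity in the text.

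The size and direction of any bias are unknown. The completer result is too favourable for all starters only if those who fail or stop improve less, which is plausible but not shown. The ratios of 1.00 to 1.43 for r between 0 and 1 illustrate assumed inputs and estimate nothing.

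One might also infer that the main findings are compromised. They need not be: the three primary outcomes can be measured before training begins. The change should be made, but it concerns one secondary outcome.

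**What to change.** 1. **Intervention:** replace exclusion from the study with the end of TAI, follow-up continuing if the patient agrees. The clinical decision to stop is unchanged.
2. **Study Protocol, last visit:** seek the final PAC-QoL, in clinic, on paper or by telephone, from everyone who began training, about 4 weeks after the last training session.
3. **Secondary Outcome Measures, item 3:** report the observed PAC-QoL change in all who began training, with the number missing, beside the change in 4-week users.
4. **Counts:** report the numbers starting, failing and stopping, using the Visit 3 and 3 bis records, preferably with a 95% interval for the share who failed or stopped.
5. **Labels:** state that repeat transit time, cost and microbiota results apply to 4-week users.

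A sensitivity analysis giving missing patients none, half or all of the completers' mean change is optional.

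**Cost:** wording in three sections and one questionnaire contact per non-completer, which is 2 to 15 contacts on the assumed 20 to 50 starters and 10% to 30% failing or stopping. There is no extra visit or X-ray. The result may look less favourable, and the failure share will be imprecise. Regression to the mean and the lack of a control group remain, so item 3 is still an uncontrolled before/after description.

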## **Primary Outcome Measure:**

Outcome 1) Incidence and prevalence of intestinal dysfunction in Multiple sclerosis. Calculation of % of patients with a PACQoL score  $\geq 32$  for items B.1 to B.6 and/or a score  $\leq 11$  for item B.7 of the questionnaire.

Outcome 2) Characteristics of intestinal dysfunction in MS. Calculation of Agachan-Wexner scores, the Cleveland Clinic Index, the Altomare Questionnaire, and the NBD Score on the patient population that report a significant impact on their QoL of problems related to their bowel management and bowel disorders in general (Score  $\geq 32$  to PAC-QoL).

Outcome 3) Intestinal transit time in SM patients with intestinal dysfunction. Calculation of % of patients with a slowed Intestinal Transit Time ( $\geq 60$  hours for women and 55 hours for men)

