**Study Protocol**

MS (Multiple Sclerosis) is the most common neurological disease involving disabilities in young adults, with Central Nervous System involvement in both the brain and spinal cord. In a recent review, its incidence in the United Kingdom is estimated at 7 new cases per 100,00 inhabitants per year, with a prevalence of about 100,000 patients. Bowel symptoms, in particular constipation and faecal incontinence, affect more than two thirds of MS patients, and have a significant impact on patients' quality of life (QoL) by significantly limiting their social, occupational and emotional life.

Recently, bowel management based on Transanal Irrigation (TAI) has also been proposed in patients with MS, but TAI efficacy on intestinal transit time and patient's compliance with TAI have not been defined yet.

The primary objective of the study is to assess the prevalence, characteristics, severity and impact on the Quality of Life of intestinal disorders in patients who consecutively refer to the neurological clinic for the diagnosis and treatment of Multiple Sclerosis at Ferrara University Hospital, Italy.

Secondary objectives are to correlate the severity and characteristics of constipation and fecal incontinence with intestinal transit time and the type of faeces evacuated according to the Bristol Stool Form Scale; to evaluate the costs in terms of the precautions (diapers, traverses, drugs, medicated clysm, etc.) and the time dedicated to the evacuation, and how these items change in relation to the use of TAI; and finally, to study the composition of the intestinal microbiota in MS patients in relation to the type of bowel characteristics, comparing it with the profile of the healthy population of the same region of origin, Emilia-Romagna, Italy.

The study proposed is a monocentric prospective observational study. The study population will be composed of patients who will consecutively refer to the Neurological Clinics of the University Hospital of Ferrara, Italy for a number of about 150 patients.

The study will consist of two phases. The first phase will be the selection of eligible patients by administering two self-filling questionnaires: PacQol (Patient Assessment of Constipation Quality of Life) and NBD (Neurogenic Bowel Dysfunction Score).

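### Outcome 1 reports quality-of-life impact on PAC-QoL as the prevalence of intestinal dysfunction, and NBD is analysed only in patients with PAC-QoL ≥32, so severity in the clinic population is not estimated

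*Combined protocol and SAP*

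**What the plan says.** The Study Protocol section sets the primary objective: to "assess the prevalence, characteristics, severity and impact on the Quality of Life of intestinal disorders" in consecutive clinic patients. Its background paragraph says which disorders are meant: "Bowel symptoms, in particular constipation and faecal incontinence, affect more than two thirds of MS patients".

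Phase 1 uses two self-completed questionnaires, "PacQol (Patient Assessment of Constipation Quality of Life) and NBD (Neurogenic Bowel Dysfunction Score").

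Under Primary Outcome Measure, Outcome 1 is headed "Incidence and prevalence of intestinal dysfunction in Multiple sclerosis". It is the percentage of patients with a PAC-QoL score ≥32 "for items B.1 to B.6 and/or a score" ≤11 on B.7. Both limbs belong to the same questionnaire. The Study population section describes PAC-QoL as recording what bowel problems do to daily life.

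Outcome 2 covers the Agachan-Wexner score, the Cleveland Clinic Index, the Altomare questionnaire "and the NBD Score on the patient population that report a significant impact on their QoL". It gives the criterion for that population as PAC-QoL ≥32, with no B.7 limb.

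The Rome III classification and the Jorge-Wexner incontinence scale come in phase 2. That phase is open to patients with PAC-QoL ≥32, and the first 50 of them are invited.

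**The concern.** The objective asks how many patients have a bowel disorder, how severe it is, and how much it affects their lives. Outcome 1 answers the third question under the label of the first. A patient with constipation or incontinence who meets neither PAC-QoL limb is counted as having no dysfunction.

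NBD is the one bowel-dysfunction score taken before selection, and it could describe severity across the clinic. The plan analyses it only after selection on impact. Two of the quantities in the primary objective, presence and severity in the clinic population, would then have no direct estimate, although relevant data are collected. Readers would probably also set the headline percentage beside published symptom prevalences, which measure something else.

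**Working it through.** The plan gives no precision or sample-size calculation for 150, and no sensitivity or specificity for the PAC-QoL cut-off, so there is no stated figure to reproduce. The check has two parts.

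**1. Tracing the definitions**

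- *Who is a case in Outcome 1?* Anyone meeting either PAC-QoL limb. No symptom criterion, incontinence item or NBD value enters the count.
- *Who enters Outcome 2?* Patients with PAC-QoL ≥32 only. A patient who is a case through B.7 alone is counted in Outcome 1 and left out of Outcome 2, so the two primary outcomes describe different groups.
- *Where else is NBD used?* In secondary outcome 1, "Correlation between Intestinal Transit Time and constipation scores in MS patients with intestinal dysfunction", and in the offer of transanal irrigation (Study Protocol). Both fall after PAC-QoL selection.
- *Is incontinence measured across the clinic?* No. The Jorge-Wexner scale and Rome III classification are phase 2 assessments.
- *Does the Statistical analysis section repair this?* No. It lists summary statistics, tests and a regression, and specifies no NBD or incontinence analysis in all phase 1 patients.
- *How does the plan describe the cut-off?* The Intervention section equates PAC-QoL ≥32 with severe impairment. Outcome 1's main limb uses the same value for any dysfunction.

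**2. Illustration of what the count could miss**

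Inputs from the documents: n = 150, and a background rate above two thirds, taken here as a true rate p = 2/3. Assumed inputs: sensitivity (Se) and specificity (Sp) of the whole Outcome 1 rule, both limbs together, for any bowel dysfunction.

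Expected percentage flagged = Se × p + (1 − Sp) × (1 − p). Number missed = (1 − Se) × p × 150.

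| Se | Missed, of 100 affected | Flagged, Sp 1.0 | Flagged, Sp 0.9 |
|---|---|---|---|
| 1.0 | 0 | 66.7% | 70.0% |
| 0.9 | 10 | 60.0% | 63.3% |
| 0.8 | 20 | 53.3% | 56.7% |
| 0.7 | 30 | 46.7% | 50.0% |
| 0.5 | 50 | 33.3% | 36.7% |

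95% half-width at p = 2/3: 1.96 × √(0.667 × 0.333 / 150) = 0.0754, or 7.5 points.

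With Sp = 1.0 the shortfall is (1 − Se) × 2/3. It equals the half-width when 1 − Se = 0.0754 / 0.6667 = 0.113, so Se ≈ 0.89.

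With Sp = 0.9, false positives add 0.1 × 1/3 = 3.3 points. The net bias is zero when (1 − Se) × 2/3 = 0.033, so Se = 0.95. Below that it is downward; above it, upward.

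**The case against.** The strongest reply is that Outcome 1 is explicit: anyone can see what is counted. The plan also describes PAC-QoL more broadly than its name suggests. Outcome 2 ties the cut-off to bowel management and bowel disorders in general, and the Study population section refers to intestinal disorders and defecation. The B.7 limb widens the case definition further. Much of this stands, and it rules out several stronger readings that a reader might infer.

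- *That incontinent patients are systematically missed.* The documents contain neither the PAC-QoL nor the NBD items. Low PAC-QoL scores in patients whose problem is incontinence are plausible but not shown, and some of these patients may well reach a limb.
- *That prevalence is biased downward by a known amount.* This would need sensitivity and specificity, which are not given. With specificity 0.9 the net bias could be zero or upward. Nor can every patient below 32 on B.1 to B.6 be treated as miscounted, because B.7 can still make that patient a case.
- *That severity cannot be related to impact at all.* PAC-QoL still varies above 32. The relation can be examined, but only over a truncated range and not for the clinic population.
- *That NBD goes unused.* It has three planned uses. What is missing is any specified use in patients with PAC-QoL <32.

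The reply does not remove the mismatch. A broader impact score is still an impact score, B.7 is part of the same questionnaire, and an explicit definition does not make the label accurate.

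**Conclusion.** The point holds as a mismatch between the primary objective and its measures. Followed as written, the plan would report quality-of-life impact as prevalence of dysfunction. It would leave patients flagged only by B.7 out of Outcome 2 and give no severity distribution for the clinic population. These conclusions rest on the definitions alone and need no assumption about test accuracy.

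The numerical consequence is not known. If specificity is high, any bias is downward. At an assumed true rate of 2/3 and specificity 1.0, it exceeds the 7.5-point half-width once sensitivity is below about 0.89, and assumed sensitivities of 0.5 to 0.9 would give 33% to 60% instead of 66.7%. This range shows how much depends on the label; it does not estimate the error. The change should be made, since the core data are already planned.

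**What to change.** In the Primary Outcome Measure section:

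1. Keep both limbs of Outcome 1, but label it *prevalence of bowel-related QoL impairment*.
2. Remove the PAC-QoL ≥32 restriction on NBD in Outcome 2. Report the NBD score distribution in all phase 1 patients, with the severity categories and the cut-off for dysfunction written into the plan before analysis. The documents currently give neither, and without a cut-off the NBD distribution is not a prevalence.
3. Cross-tabulate NBD with Outcome 1 status. This shows how many patients have dysfunction without impact, and the reverse.
4. State that the incontinence scale and Rome III classification describe only phase 2 patients, so they give no clinic-wide prevalence of incontinence. Moving the incontinence scale into phase 1 would supply one, at the price of one more questionnaire, but this is optional.

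The Study population section says that every patient receives PAC-QoL and does not mention NBD. One sentence there should confirm that every phase 1 patient completes both.

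The cost is wording and one extra table. Phase 2 entry and treatment are unchanged.
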